10.8.2. Additional Analysis to Support Paediatric Extrapolation Strategy

10.8.2.1. Population-PK analysis

In addition, to confirm that paediatric PK data from 6-11 years old subjects can be predicted from the adult PK model, the most recent population PK model will also be applied directly to the dataset without estimation (e.g. maxevals=0 in NONMEM) and predictions generated against which the model will be validated prospectively using appropriate goodness of fit tests. For example the Cramér–von Mises and Kolmogorov–Smirnov tests are accepted methods of comparing Empirical Distribution Functions for model and data (i.e. PK concentrations) to evaluate whether independent observations (observed PK concentrations from the study) are adequately described by a model.

The current PK model consists of a two-compartment pharmacokinetic model with first-order absorption and elimination. Bodyweight is incorporated into the model using allometry with fixed physiological allometric exponents of 0.75 and unity for clearance and volumes, respectively. Albumin and creatinine clearance are also included as covariates of mepolizumab clearance on physiological grounds, however their effects are small and not of clinical relevance.

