7. STUDY ASSESSMENTS AND PROCEDURES

Protocol waivers or exemptions are not allowed with the exception of immediate safety concerns. Therefore, adherence to the study design requirements, including those specified in the Time and Events Table, are essential and required for study conduct.

This section lists the procedures and parameters of each planned study assessment. The exact timing of each assessment is listed in the Time and Events Tables ([Table 3](#) and [Table 4](#)).

Table 3 Time and Events Table - Pharmacokinetic/Pharmacodynamic Phase (Part A)

Procedure	Pre-Screen ¹	Screening	Treatment Period				Exit Visit ³	Follow-up		Early Withdrawal
Visit Number	0	1	2	3	4	5	6	7	8 ⁸	
Week of Study (visit window \pm 3 days, \pm 1 day Visit 5))	Prior to or same day as Visit 1	(up to 14 days prior to Visit 2)	0	4	8	9	12	16	20	
Subject Screen										
Informed consent	X									
Inclusion and exclusion criteria		X	X							
Demography	X									
Medical history, including bronchodilator reversibility history ⁴		X								
Past and current medical conditions		X								
Asthma exacerbation history		X								
Safety Assessments										
Concomitant medications	X	X	X	X	X	X	X	X	X	X
Hematology (including eosinophils)		X	X	X	X	X	X	X	X	X
Clinical Chemistry		X		X	X		X		X	X
12-lead ECG		X		X			X			X
Vital signs		X	X	X	X	X	X	X	X	X
Bodyweight			X							
Brief physical examination		X								
Adverse events		X	X	X	X	X	X	X	X	X
Cardiovascular events		X	X	X	X	X	X	X	X	X
Liver events		X	X	X	X	X	X	X	X	X
Laboratory Assessments										
Urinalysis		X							X	X
Pregnancy Test		U	U ⁵	U ⁵	U ⁵		U	U	U	U
HBsAg and hepatitis C antibody		X ⁶								
Serum IgE (total)			X ⁵							
PK blood sample				X ⁵	X ⁵	X	X	X	X	X

Procedure	Pre-Screen ¹	Screening	Treatment Period				Exit Visit ³	Follow-up		Early Withdrawal
Visit Number	0	1	2	3	4	5	6	7	8 ⁸	
Week of Study (visit window \pm 3 days, \pm 1 day Visit 5))	Prior to or same day as Visit 1	(up to 14 days prior to Visit 2)	0	4	8	9	12	16	20	
IL5 serum sample			X ⁵				X			
Blood sample for immunogenicity ^{2,7}			X ⁵					X	X ²	X
Outcomes Assessments										
FEV1		X	X	X			X	X	X	X
ACQ-7			X	X	X		X	X	X	X
C-ACT			X	X	X		X	X	X	X
Assessment of exacerbation	X	X	X	X	X	X	X	X	X	X
Investigational Product										
Mepolizumab SC dose administered			X	X	X					
Study Administration										
Email to GSK Operational Lead	X	X	X	X	X	X	X	X	X	X
Complete eCRF	X	X	X	X	X	X	X	X	X	X

1. Pre-screen must be completed prior to or on the same day as Screen Visit.

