2.4. Statistical Hypotheses

Formal hypothesis testing will not be performed for this study. An estimation approach will be adopted to evaluate the objectives.

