- Summary = Represents TFL related to any summaries (i.e. descriptive statistics) of the observed raw data/predicted data.
- Individual = Represents FL related to any displays of individual subject (observed raw data/predicted data).

^[1] To be presented as a Ratio to Baseline

^[2] Kaplan-Meier estimates

^[3] Model Predicted Mepolizumab Individual Plasma Concentration Time Profiles with Individual Observed Plasma Concentrations and Plasma Concentration Population Prediction from Final Model by Treatment

^[4] Model Predicted Mepolizumab Individual Plasma Concentration Time Profiles with Individual Observed Plasma Concentrations and Plasma Concentration Population Prediction from Final Model by Subject

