10.8.2.2. Population-PK/PD analysis

Likewise, to confirm that paediatric blood eosinophil count data from 6-11 years old subjects can be predicted from the adult PK/PD model, the most recent population PK/PD model will be applied directly to the dataset without estimation (e.g. maxevals=0 in

NONMEM) and predictions generated against which the model will be validated prospectively using appropriate goodness of fit tests as described above (using the observed data from the study).

The population PK/PD model consists of an indirect response model parameterised in term of baseline blood eosinophil count (KRO), rate of elimination of eosinophils in the blood (Kout), concentration resulting in 50% of maximum drug effect (IC_{50}) and maximum effect (I_{max}). Observed baseline blood eosinophil count is included as covariates of both predicted baseline and mepolizumab inhibitory response; and disease for predicted baseline blood eosinophil count.

If a blood eosinophil count of zero is reported, it will be imputed with half of the lowest possible blood eosinophil count, where applicable, prior to log transforming the data (Note: this imputation has typically been $0.5 * 0.01 \text{ GI/L} = 0.005 \text{ GI/L}$ for previous mepolizumab studies).

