10.10. Appendix 10: List of Data Displays

10.10.1. Data Display Numbering and Priority

10.10.1.1. Part A

The following numbering will be applied for RAP generated displays:

Section	Tables	Figures
Study Population	1.1 to 1.22	Not applicable
Pharmacokinetic Analysis	2.1 to 2.11	2.1 to 2.15
Efficacy Analysis	2.12 to 2.24	2.16 to 2.23
Safety Analysis	3.1 to 3.53	3.1 to 3.2
Section	Listings	
ICH Listings	1 to 43	
Other Listings	44 to 51	

Delivery [Priority] ^[1]	Description
SAC1	Part A Statistical Analysis Complete 1
SAC2	Part A Statistical Analysis Complete 2 (Further analyses supportive of mepolizumab paediatric extrapolation)

NOTES:

1. Indicates priority (i.e. order) in which displays will be generated for the respective reporting effort (Part A/Part B).

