10.10.2.2. Pharmacokinetic Tables

No.	Population	IDSL / TST ID / Example Shell	Title	Programming Notes	Deliverable [Priority]
PK (Primary Endpoint)					
2.1.	PK	DBRL1/DBRN1	Summary of Plasma Mepolizumab Pharmacokinetic Concentration-Time Data (observed and predicted)	Shell from Respiratory display standards [Only the summary of untransformed data will be included] Summary by mepolizumab dose group and mepolizumab overall.	SAC1
2.2.	PK	DBRL4/DBRN4	Summary Statistics of Individual Model Predicted and Plasma Mepolizumab Pharmacokinetic Parameters (non-transformed and log-transformed)	Include untransformed and log-transformed summary statistics. Include 95% CIs for geometric mean. Summary by mepolizumab dose group and mepolizumab overall	SAC1
2.3.	PK		Description and Evaluation of Key PK Models Tested	Provided by CPMS	SAC1
2.4.	PK		Population PK Parameter Estimates with 95% CI of Final PK Model	Provided by CPMS Summary for mepolizumab overall	SAC1
2.5.	PK		Demographics Summary (only if different from study population)	Provided by CPMS	SAC1
2.6.	PK		Samples Summary	Provided by CPMS	SAC1
PK (Secondary Endpoint)					
2.7.	PK		Population estimate and 90% CI of bodyweight-adjusted clearance in paediatric subjects together with historic value in adults around which a proposed 80-125% interval is applied.	Summarise mepolizumab overall Provided by CPMS	SAC1
PK (Exploratory Analysis)					
2.8.	PK		Goodness of Fit Test Results	Provided by CPMS	SAC2

No.	Population	IDSL / TST ID / Example Shell	Title	Programming Notes	Deliverable [Priority]
PKPD (Exploratory Analysis)					
2.9.	PKPD		Demographics Summary (only if different from study population)	Provided by CPMS	SAC2
2.10.	PKPD		Samples Summary	Provided by CPMS	SAC2
2.11.	PKPD		Goodness of Fit Test Results	Provided by CPMS	SAC2

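### Do repeated PK samples per child invalidate the Kolmogorov–Smirnov and Cramér–von Mises checks of the adult model?

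*SAP*

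**What the plan says.** SAP 10.8.2.1 adds an analysis in support of the paediatric extrapolation. The latest adult PK model is run on the children's data with its parameters held fixed, predictions are generated, and the model is judged by suitable goodness-of-fit tests. KS and CvM are offered as examples of accepted ways of "comparing Empirical Distribution Functions for model and data (i.e. PK concentrations"), used "to evaluate whether independent observations (observed PK concentrations from the study) are adequately described by a model". SAP 10.8.2.2 treats eosinophil counts in the same way: the adult PK/PD model is to be "validated prospectively using appropriate goodness of fit tests as described above".

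Four things are left open:
- whether the predictions are population or individual;
- whether the tested values are concentrations or prediction errors;
- whether values are pooled, taken by visit or decorrelated within child;
- where the reference distribution comes from.

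No level or pass rule is given, and SAP 2.4 states: "Formal hypothesis testing will not be performed for this study".

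The results go to Tables 2.8 and 2.11, each titled "Goodness of Fit Test Results", under exploratory headings. They belong to the delivery described as "Part A Statistical Analysis Complete 2 (Further analyses supportive of mepolizumab paediatric extrapolation"). In Protocol Table 3, the row "PK blood sample" is marked at weeks 4, 8, 9, 12, 16 and 20, plus early withdrawal.

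**The concern.** Six concentrations from one child share that child's clearance and volume, so they are correlated. The usual KS and CvM critical values are derived for independent values. If the values are pooled as though they were independent, the nominal level is lost. The SAP's use of the word independent can be read as overlooking this.

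The direction of the error also depends on choices the SAP leaves open. Pooled population prediction errors would reject a correct model too often. Individual post-hoc predictions would adapt to each child and could hide a real difference between children and adults. The section's purpose is to confirm that paediatric PK follows from the adult model, so either error could mislead a reader of Tables 2.8 and 2.11.

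**Working it through.** **1. No figure to reproduce.** The SAP gives no level, critical value or power for these tests.

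**2. Inputs from the documents.** Six scheduled samples per child (Protocol Table 3). About 28 children treated and 20 evaluable (Protocol 4.3). Half-life about 20 days (Protocol 2.2.2). Adult CL/F 0.29 L/day (Protocol 9.2). Allometric exponents 0.75 and 1 (SAP 10.8.2.1). Doses at weeks 0, 4 and 8.

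**3. Assumptions, because the documents give none.** Nominal 5% level; one-compartment subcutaneous model; absorption rate 0.4/day; weights 18–58 kg; between-child log-SD of clearance 0.2–0.4 and of volume 0.15–0.3; residual log-SD 0.3–0.1.

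**4. Strength of the correlation.** Pooling gives 20 × 6 = 120 values. Under these assumptions the mean within-child correlation of log concentrations is 0.45–0.85. The design effect is 1 + (6 − 1) × 0.45 = 3.25 up to 1 + (6 − 1) × 0.85 = 5.25. As a rough guide, 120 values carry the information of 120/3.25 ≈ 37 down to 120/5.25 ≈ 23.

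**5. Rejection of a correct adult model.** 20 children, % of trials, KS / CvM (1000 trials per setting; 500 for two-sample CvM). Columns give the log-SDs of clearance / volume / residual.

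| Version of the test | 0.2/0.15/0.3 | 0.2/0.15/0.2 | 0.3/0.2/0.15 | 0.4/0.3/0.1 |
|---|---|---|---|---|
| Population percentiles, pooled, not decorrelated | 25.9 / 28.5 | 33.3 / 35.0 | 47.0 / 47.2 | 50.3 / 49.0 |
| Decorrelated within child, then pooled | 4.7 / 5.0 | 4.5 / 4.3 | 4.9 / 4.7 | 5.6 / 5.7 |
| One visit only (KS) | 4.7 | 3.7 | 5.2 | 4.4 |
| Observed vs population-predicted concentrations | 0.3 / 0.2 | 0.0 / 0.0 | 1.0 / 0.4 | 6.2 / 4.6 |
| Observed vs post-hoc individual predictions | 0 / 0 | 0 / 0 | 0 / 0 | 0 / 0 |

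With 28 children, run for the two middle settings, the pattern is the same. KS rejects 33.2% and 47.4% for undecorrelated percentiles, and 4.4% and 5.1% after decorrelation.

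**6. Detection of a real difference.** True clearance 1.25 times the adult value, 20 children, two middle settings, KS / CvM (500 trials).

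| Version of the test | 0.2/0.15/0.2 | 0.3/0.2/0.15 |
|---|---|---|
| Observed vs population-predicted concentrations | 73.2 / 83.8 | 74.0 / 74.8 |
| Decorrelated within child | 91.0 / 94.4 | 35.8 / 41.4 |
| One visit only (KS) | 92.8 | 77.0 |
| Observed vs post-hoc individual predictions | 0 / 0 | 0 / 0 |

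**7. A second run.** This also used 20 children and assumed variances, and it allowed model-simulated as well as population-predicted concentrations as the comparator. The comparison of concentrations rejected a correct model in 0–14% of trials and detected the 25% shift in 73–86%. Undecorrelated population errors gave 24–69% false rejection.

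**8. Setting the results against the text.** SAP 10.8.2.1 names concentrations as the thing compared and model predictions as the comparator. Its nearest literal form is the fourth row of the first table, which is mostly conservative and retains power. The two badly behaved rows each need a step the section does not state: pooling prediction errors under standard critical values, or using individual predictions.

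**9. The word independent.** The section describes a fixed model validated prospectively and glosses the observations as the study's own concentrations. Data not used to build the model is the natural meaning. It does not remove the within-child correlation, but it is not a claim that a child's six samples are mutually independent.

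**The case for a change.** The strongest case for a change is the post-hoc branch. SAP Table 7 footnotes for the exploratory PK displays list both kinds of prediction: "Model Predicted Mepolizumab Individual Plasma Concentration Time Profiles with Individual Observed Plasma Concentrations and Plasma Concentration Population Prediction from Final Model by Treatment". If individual predictions entered the test it could hardly fail. In the runs above it never rejected at 1.25 times adult clearance, nor at 1.5 times. KS and CvM are the only tests named, SAP 10.8.2.2 relies on them, predictability from the adult model is a stated aim in Protocol 2.1, and a clarifying sentence would be cheap.

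Two parts of this stand. A post-hoc version would be uninformative, and p-values from undecorrelated pooled errors would be misleading. The inference that the plan does either is weaker. The footnotes describe concentration–time plots, not test inputs. Where the SAP means post-hoc individual estimates it says so (Section 7.1.1); Section 10.8.2.1 does not.

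Nor is one remedy clearly best. In a simpler normal-score simulation (20 children, shift of 0.5 total SD, within-child correlation 0.5), a reference distribution simulated by child had KS power 79% against 59% for decorrelated errors. The simulated version, however, takes the adult between-child variance as given: it rejects 7–12% instead of 5% if the children's between-child SD is 25% larger with no mean shift. That is a modelling judgement best made with the data and model in hand.

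The eosinophil extension raises the same question, with a model that already uses the observed baseline as a covariate. Its effect was not quantified.

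**Conclusion.** The gap is real but does not call for a change to the plan. The SAP commits to suitable tests and gives examples; it does not fix an invalid procedure. Versions that fit its text hold their level (3.7–5.7% in the settings shown) or are mostly conservative (0–6%, and up to 14% in the second run). The 26–50% false rejection belongs to an implementation the SAP does not specify.

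The consequence is also limited. There is no level or decision rule, which is consistent with SAP 2.4. Only exploratory Tables 2.8 and 2.11 carry the results. The same delivery includes goodness-of-fit plots, observed/predicted profiles and visual predictive checks (Figures 2.7–2.14), which would expose a clearance shift that a poorly chosen test missed. The primary PK estimates (SAP 7.1) and the clearance comparison against 0.18–0.28 L/day with its 90% CI (SAP 8.1.1) do not use these tests.

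The percentages rest on assumed variances, an assumed 5% level and a simplified PK model. The contrast between the undecorrelated and decorrelated versions, and the insensitivity of the post-hoc version, held in every setting tried. The conclusion assumes that the modellers use population predictions, account for repeated samples within child and read any p-value as descriptive.

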10.8.2.2. Population-PK/PD analysis

Likewise, to confirm that paediatric blood eosinophil count data from 6-11 years old subjects can be predicted from the adult PK/PD model, the most recent population PK/PD model will be applied directly to the dataset without estimation (e.g. maxevals=0 in

NONMEM) and predictions generated against which the model will be validated prospectively using appropriate goodness of fit tests as described above (using the observed data from the study).

The population PK/PD model consists of an indirect response model parameterised in term of baseline blood eosinophil count (KRO), rate of elimination of eosinophils in the blood (Kout), concentration resulting in 50% of maximum drug effect (IC_{50}) and maximum effect (I_{max}). Observed baseline blood eosinophil count is included as covariates of both predicted baseline and mepolizumab inhibitory response; and disease for predicted baseline blood eosinophil count.

If a blood eosinophil count of zero is reported, it will be imputed with half of the lowest possible blood eosinophil count, where applicable, prior to log transforming the data (Note: this imputation has typically been $0.5 * 0.01 \text{ GI/L} = 0.005 \text{ GI/L}$ for previous mepolizumab studies).

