9.2. Sample Size Considerations

The sample size was determined by the number of subjects needed for the PK and PD evaluations of Part A of the study, based on previous PK/PD studies. A pediatric population-PK trial simulation (GSK Document Number [2014N223495_00](#)) was used to determine the Root Mean Square Error (RMSE, i.e. standard deviation) in estimated exposure ($AUC_{(0-\infty)}$) as a function of sample size, pharmacokinetic sampling scheme and model assumptions. Based on 1000 trial simulations per scenario, a sample size of 16-32 subjects is sufficient to maintain precision in exposure estimation (and hence bodyweight-adjusted clearance) below 20%, (as compared with the guideline 40%), providing five pharmacokinetic samples (including one close to Tmax) are collected and four parameters are fixed from adult values in the population-PK model.

For blood eosinophils it is expected that this trial will have a similar residual variance to that observed in the MEA115588 trial, where a residual SD of 0.7867 on the log transformed scale was observed. Based on this assumption, a total of 20 subjects should provide sufficient precision for the 95% confidence interval for the ratio to baseline to lie within a ratio of 50% of the observed value. For example if the observed ratio to baseline for blood eosinophils is 0.14, the reduction observed in trial MEA115588, the 95% confidence interval is expected to be from 0.09 to 0.20.

With regards to the pre-planned secondary analysis, the trial simulations also showed that for the proposed sample size and sampling scheme, 80% of simulated trials yielded a bodyweight-adjusted apparent clearance with 90% confidence limits falling within the bounds 0.8 – 1.25 of the adult apparent clearance value (CL/F of 0.29 L/day). This

precision is deemed sufficient for extrapolation purposes from adults to pediatric subjects aged 6 to 11 years supported by this study (GSK Document Number [2014N223495_00](#)).

Patients who complete Part A and who meet the eligibility criteria for Part B will be allowed to participate in Part B and no specific sample size requirements are defined.

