2.3. Study Design

Overview of Study Design and Key Features	

Part A:
 
■ Mepolizumab [100mg (subjects with body weight ≥ 40 kg) OR 40mg (subjects with body weight < 40 kg)
	
Design Features	
Part A:
 
 This is a multi-centre, open-label study that will assess the pharmacokinetics and pharmacodynamics of three 4-weekly doses of mepolizumab, either 40 or 100mg SC depending on subject bodyweight, administered subcutaneously to subjects with severe eosinophilic asthma aged 6-11 years. Approximately 40 male or female subjects with severe eosinophilic asthma, aged 6 to 11 years inclusive at screening (Visit 1), will be screened to achieve approximately 28 eligible subjects entering the treatment phase to allow availability of 20 evaluable subjects; with a minimum of six subjects enrolled in the < 40 kg bodyweight group. An evaluable subject is defined to be a subject who has received all three doses of mepolizumab and has had all PK and PD assessments completed through to Visit 6 (week 12). 
Part B:
 
 This is a long-term safety / pharmacodynamic phase in which extended treatment for a further 52 weeks will be offered on an optional basis to those subjects eligible for continued treatment. Subjects will receive either 40 or 100mg depending on subject bodyweight, administered SC every 4 weeks to subjects with severe eosinophilic asthma aged 6-11 years. At the end of the 52 weeks extended treatment in Part B, subjects will have an Exit Visit 4 weeks after last dose and a Follow-Up visit 12 weeks after last dose. All subjects who completed Part A and meet the eligibility criteria for Part B will be allowed to participate in Part B. Countries participating in this study include: Japan, Poland, United States and United Kingdom.
Dosing	
Part A:
 
 Mepolizumab will be administered as either 40mg (subjects < 40kg at

Overview of Study Design and Key Features	

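### The planned check that the adult model predicts children's eosinophil counts tests for misfit and sets no measure of agreement, so a non-significant result in 20 to 28 children would be weak support

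*SAP*

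**What the plan says.** SAP 10.8.2.2 gives the purpose of the population PK/PD analysis as "to confirm that paediatric blood eosinophil count data from 6-11 years old subjects can be predicted from the adult PK/PD model". The adult model is run on the children's data with no parameters estimated and is to be "validated prospectively using appropriate goodness of fit tests as described above". The reference is to SAP 10.8.2.1, which sets out the same approach for concentrations: "For example the Cramér–von Mises and Kolmogorov–Smirnov tests are accepted methods of comparing Empirical Distribution Functions". That section describes the tests' use as "to evaluate whether independent observations (observed PK concentrations from the study) are adequately described by a model".

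For eosinophils the SAP states no significance level, pass/fail rule or margin. Of the three PKPD tables in SAP 10.10.2.2, Tables 2.9 and 2.10 cover demographics and samples, so Table 2.11 (goodness-of-fit test results) is the only one that reports a result. SAP 10.10.2.3 adds observed/predicted profiles by treatment and by subject, goodness-of-fit plots and a visual predictive check (Figures 2.11 to 2.14). All are labelled exploratory and belong to the second delivery, SAC2.

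SAP 2.4 says: "Formal hypothesis testing will not be performed for this study. An estimation approach will be adopted to evaluate the objectives". For clearance, SAP 8.1.1 does plan an estimate: a point value and 90% CI set beside the adult value and an 80-125% interval.

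**The concern.** The purpose is to show agreement, but the named tests look for disagreement. A non-significant result can mean that the model predicts well, or only that there are too few or too noisy data to show that it does not. With a small trial, the second explanation is a live one.

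This matters because SAP 10.8.2 is there to support extrapolation from adults to children, and that argument needs both similar exposure and similar response. Clearance is reported as an estimate with an interval against a stated range. The eosinophil prediction gets test results and plots, but no number for how far observed counts sit from predicted ones and no interval around such a number. A moderate error could therefore pass without its plausible size being reported.

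**Working it through.** **Inputs**
- Log-scale SD: Protocol 9.2 reports that in trial MEA115588 "a residual SD of 0.7867 on the log transformed scale was observed".
- Number of children: the plan is "to achieve approximately 28 eligible subjects entering the treatment phase to allow availability of 20 evaluable subjects". The PKPD population (SAP section 4) is not restricted to evaluable children, so n = 20 and n = 28 bracket it.
- Post-dose counts per child in Part A: six, at weeks 4, 8, 9, 12, 16 and 20 (SAP 10.2.1).
- Assumed, not in the documents: a two-sided 5% level; log counts normal around the prediction with SD 0.7867; a pure multiplicative shift as the error; one value per child.

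**The plan's own figure.** Protocol 9.2 expects a 95% CI of 0.09 to 0.20 around a ratio to baseline of 0.14 with 20 children.
- SE = 0.7867/√20 = 0.1759. With t(19) = 2.093, the half-width is 0.368 and the factor exp(0.368) = 1.445.
- The interval is 0.14/1.445 to 0.14 × 1.445, that is 0.097 to 0.202.
- The upper limit agrees. The lower limit rounds to 0.10 rather than 0.09, but 0.09 follows if the unrounded ratio is about 0.135 to 0.137. I treat the figure as reproduced within rounding.

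**How often the tests miss a real error.** Each child's log deviation from prediction is drawn from a normal distribution with mean log(ratio) and SD 0.7867. The one-sample tests are run against the fully specified model (ratio 1), with simulated 5% critical values and 100,000 trials per case. Entries are the share of trials with a non-significant result.

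| True observed/predicted ratio | n=20 KS | n=20 CvM | n=28 KS | n=28 CvM |
|---|---|---|---|---|
| 1.25 | 81% | 78% | 75% | 70% |
| 1.5 | 49% | 42% | 35% | 27% |
| 1.75 | 22% | 15% | 10% | 6% |
| 2 | 7% | 4% | 2% | 1% |

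At a 10% level the n = 20, 1.5-fold entries fall to about 36% and 30%.

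**If repeated counts were pooled.** Treating 20 × 6 = 120 counts as independent breaks the tests' own condition. With an assumed within-child correlation of 0.3, 0.5 or 0.7, a correct model would be rejected in about 19-20%, 29-31% or 39% of trials instead of 5%. The error then runs the other way, towards false alarm.

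**What an estimate would give.** The 90% CI factor for the geometric mean ratio is exp(t × 0.7867/√n).
- n = 20: 1.729 × 0.1759 = 0.304, factor 1.36.
- n = 28: 1.703 × 0.1487 = 0.253, factor 1.29.

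**The case against.** A reader might infer that a non-significant test would count as proof of predictability. The documents do not say so. *Confirm* appears as a purpose, no threshold is attached to the tests, they are introduced as examples, and SAP 2.4 rules out formal hypothesis testing. A reader might also infer that the tests are the only check on the eosinophil prediction. They are not: the profiles and the visual predictive check show the direction and rough size of misfit, and the analysis is exploratory.

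The primary eosinophil analysis (SAP 7.2) is already an estimate, the geometric mean ratio to baseline with a 95% CI. If the true ratio were 1.5 × 0.14 = 0.21, that CI would be expected to run from about 0.145 to 0.30 with 20 children, and it would exclude 0.14 in about 59% of trials (75% with 28). So a 1.5-fold difference would not be hidden. The clearance comparison has no explicit pass/fail rule either. Finally, 0.7867 comes from another trial, while the PK/PD model conditions on each child's baseline count, so its residual spread may differ.

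All of this stands, and it limits the point. It does not supply what is missing. The ratio to baseline is not compared with the model's predictions for these children, the plots have no stated reading rule, and no planned output puts an interval on the prediction error.

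**Conclusion.** The point holds as a gap in method and wording, not as a claim that the sponsor will misread a p-value. SAP 10.8.2.2 sets out to confirm agreement with tests whose null is agreement, and gives neither an acceptance rule nor a measure of disagreement. At the planned size those tests reliably catch a 2-fold error, but miss a 1.5-fold error in roughly a quarter to a half of trials and a 1.25-fold error in roughly 70% to 80%. These rates depend on the assumed 5% level, on the SD carrying over, and on one value per child; pooling repeated counts would change them and invalidate the tests.

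Protocol 9.2's 50% figure should not be read as an equivalence margin. It is a precision target for a 95% CI around the observed ratio to baseline, and no document says what adult-to-child difference in eosinophil response would matter for extrapolation. The improvement is worth making because it is cheap and follows the SAP's own stated estimation approach.

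**What to change.** - In Table 2.11, add the child-level geometric mean ratio of observed to adult-model-predicted count at Week 12, with its 90% CI. Use the model's population prediction given the child's covariates and dosing, not one already informed by that child's own post-dose counts. One value per child avoids the independence problem.
- Judge predictability from that estimate and interval. Keep the goodness-of-fit tests and the visual predictive check as diagnostics; they remain useful for spread and shape, which a mean ratio does not cover. State how repeated counts are handled in any test.
- Replace *confirm* with *assess* in SAP 10.8.2.2.
- If the sponsor wants an equivalence margin, it should be justified and fixed before SAC2.

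The cost is one output line and a wording change. The downside is a wide interval, about a factor of 1.36 either way with 20 children and 1.29 with 28, so the result may have to be reported as inconclusive. As an illustration only, with limits of 1/1.5 to 1.5 and a perfectly correct model, the 90% CI would fall inside in about 44% of trials at n = 20 and 69% at n = 28.
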